## 9. SAFETY

All safety analyses will be analyzed for the Safety Population. The AEs and SAEs will be collected from the screening visit through the end of the study period.

Safety will be assessed based on the incidence of treatment emergent adverse events (TEAEs) and clinically relevant changes in vital signs, clinical laboratory assessments (hematology, serum chemistry, and urinalysis), physical and neurological examinations, ECG tests. Each safety parameter will be listed by subject.

### 9.1. Adverse Event Preferred Term and Body/Organ System Summary Tables

#### 9.1.1. Summaries of Adverse Event Incidence Rates for All Subjects

All AEs will be coded to System Organ Class (SOC) and Preferred Term using the Medical Dictionary for Regulatory Activities (MedDRA®). Note, the terms AEs and TEAEs are used interchangeably in this SAP and unless otherwise specified refer to TEAEs.

A Treatment Emergent Adverse Event (TEAE) is defined as an AE that occurs for the first time after initiation of treatment or if it had occurred prior to treatment, it worsens in severity after initiation of treatment.

An overall summary by treatment group NurOwn® and Placebo that includes the number and percentage of subjects who experienced at least one TEAE for the following categories: TEAEs, serious TEAEs, treatment-related TEAEs, TEAEs by severity, TEAEs leading to treatment withdrawal, and TEAE leading to death and/or study discontinuation and procedure related TEAEs will be presented. When appropriate, a total column may appear as the last column.

Separate summaries with SOC and PT will be provided for the following categories of AEs:

- TEAEs
- TEAEs by severity
- Treatment-related TEAEs
- Serious TEAEs
- Procedure-related TEAEs
- Procedure-related TEAEs by severity
- All TEAEs excluding procedure-related TEAEs

The above summaries will include the number of events as well as number and percentage of subjects experiencing at least one TEAE in each SOC and Preferred Term. To count the number of participants with any TEAEs, a subject who experiences multiple TEAEs within the same SOC will be counted only once for that SOC (if the TEAEs are coded to the same Preferred Term). A subject who experiences multiple TEAEs coded to the same Preferred Term within the same SOC will be counted only once for that Preferred Term. The number and percentage of subjects experiencing any TEAE will also be provided. All percentages will use the number of subjects in the safety population within that treatment group as the denominator. In the summaries, SOCs will be sorted by alphabetical order and Preferred Terms within SOCs will be sorted by descending order of incidence in NurOwn® treatment group.

Treatment-emergent AEs will also be summarized by maximal severity (Mild, Moderate, Severe, or Potentially Life-Threatening). Summary table will include the number and percentage of subjects experiencing at least one TEAE in each SOC, Preferred Term, and severity.

The relation of TEAEs to study drug will be summarized by their relatedness (definite, probable, possible, unlikely and not related).

For subjects who discontinue the study, any SAEs reported through 12 weeks following their last transplantation prior to discontinuation will be included in the safety database.

A listing will provide details of all subjects who experience a SAE, died during the study or experienced an AE that led to discontinuation from the study.

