This is a Phase 3 randomized, double-blind, placebo-controlled multicenter study that will be conducted in approximately 200 participants with early ALS at multiple investigational study sites. After providing informed consent, each participant will be observed over an approximately 18-week screening period and undergo monthly ALSFRS-R scores along with safety assessments and recording of concomitant medications and adverse events (AEs) will be obtained. During this period of time, participants meeting the inclusion and exclusion criteria will be randomized and a week later will undergo bone-marrow aspiration. MSC of the participants randomized to the treatment group will be isolated, propagated for approximately 2 weeks and then cryopreserved. Approximately 2 weeks prior to each treatment, MSC will be thawed, propagated and induced into MSC-NTF cells. Participants will undergo a total of three intrathecal (IT) transplantations with NurOwn® (MSC-NTF cells) or matching placebo. The first transplantation will be at Visit 6 (Week 0) approximately 18 weeks after screening, with the subsequent transplantations at Visit 9 (Week 8) and Visit 11 (Week 16). Following the third and last treatment, participants will be followed for three additional monthly visits (through week 28) during which the ALSFRS-R assessment, neurological examination, biomarkers assessment, assessment of blinding, safety assessments and recording of concomitant medications and AEs will be performed.

See study scheme below and schedule of assessments in [Table 1](#) in [Section 1.15](#) Appendix 1

In consideration of contingency measures implemented at participating investigative sites due to the outbreak of the Coronavirus Disease 2019 (COVID-19) pandemic, and to minimize or eliminate immediate hazards or to protect the life and well-being of research participants (e.g., to limit exposure to COVID-19), some study visits may be rescheduled and/or conducted remotely according to the implemented institutional policies at individual sites, until such a time when investigational sites are able to fully comply with the schedule of assessments.

Study Schematic

Number of sites

This is a multi-center study to be conducted at six Medical Centers in the US.

Treatments

Intrathecal administrations of NurOwn® (MSC-NTF cells) or excipient will be given at Visit 6 (Week 0), Visit 9 (Week 8) and Visit 11 (Week 16).

Randomization

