The second Phase 2a trial was a multicenter study conducted in U.S in 48 patients with early ALS to evaluate the safety and efficacy of NurOwn® (MSC-NTF cells) administered as single dose through a combination of IT and IM routes at a dose of 100×10^6 to 125×10^6 cells compared to placebo. The safety profile of the single dose of NurOwn® (MSC-NTF cells) was well tolerated with majority of AEs being mild or moderate. Significant improvement was observed in the total ALSFRS-R scores based upon percent improvement in slope, post-transplantation compared to pre-transplantation through the 24-week follow-up period.

The purpose of the proposed BCT-002 Phase 3 study is to evaluate the efficacy and safety of three successive administrations of intrathecal injections of NurOwn® (MSC-NTF cells) as compared to placebo given every two months to participants with ALS (ALSFRS-R ≥ 25 at the Screening Visit). The primary and some secondary efficacy endpoints will be assessed based upon improvement in ALSFRS-R scores. Blood and CSF samples will be collected for biomarker analyses and DNA will be collected to identify specific ALS mutations and ALS related genes that may reveal important prognostic variables in post hoc analyses (Van den Berg, et al 2019).

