1.3.3.2. Intrathecal Transplant Procedure

Participants will undergo a lumbar puncture (Spinal needle 20GA 3.50 IN (0.9 x 90 mm)) followed by IT injection of cells or placebo (Dulbecco Modified Eagle Medium, DMEM; Figure 2). IT injection is to be performed by an unblinded site team/physician that will not have further contact with the study participants or with the investigator and blinded site staff. The detailed transplantation procedure is provided in [Appendix 5](#).

Participants will be eligible for their 2nd and 3rd treatments if, in the judgment of the study team, there are no medical contraindications to proceeding.

[figure not shown]

Figure 2 Study groups flowchart

Diagram delineating placebo and cells transplantation in the treatment and placebo groups.

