## 2. INTRODUCTION

Amyotrophic lateral sclerosis (ALS) is a fatal, progressive, neurodegenerative disease characterized by motor neuron cell death in the brain and spinal cord, accompanied by rapid loss of muscle control and eventual complete paralysis. There is currently no available treatment to prevent its progressive course, and life expectancy of patients is usually 3 to 5 years after diagnosis.

The purpose of the BCT-002 Phase 3 study is to evaluate the efficacy and safety of three repeated administrations of NurOwn® (MSC-NTF cells) as compared to placebo delivered intrathecally every two months to participants with ALS (ALSFRS-R  $\geq$  25 at the Screening Visit).

The primary and key secondary efficacy endpoints will be assessed based upon improvement in ALSFRS-R scores. Blood and CSF samples will be collected for biomarker analyses and DNA will be collected to identify specific ALS mutations and ALS related genes that may reveal important prognostic variables in post hoc analyses.

The current study is a 1:1 randomized, double-blind, placebo-controlled multicenter study. The control group will be administered placebo (excipient). It is expected that approximately 100 participants in each the NurOwn® (MSC NTF cells) and placebo arms will provide an adequate number of participants in order to demonstrate a higher proportion of participants in the MSC-NTF group responding to treatment compared to Placebo.

The purpose of this statistical analysis plan (SAP) is to describe the planned analyses and data displays to be included in the Clinical Study Report (CSR) for Protocol BCT-002-US.

This SAP was developed in accordance with the ICH E9 guideline and current best practices for statistical analyses of Phase III clinical trials.

The first draft of the SAP was submitted to the FDA in November 2017 prior to the first subject being dosed. This final version incorporates feedback received from the FDA and additional details related to the analyses.

Any additional changes to the SAP such as finalizing the EE populations, additional analyses planned, etc. will be made prior to database lock and unblinding of the study data and captured in an appendix to the SAP.

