## 3. STUDY OBJECTIVES AND ENDPOINTS

### 3.1. Study Objectives

The goal of this study is to determine the efficacy and safety of repeat administrations of NurOwn®, autologous Mesenchymal Stem Cells Secreting Neurotrophic Factors (MSC-NTF cells) as compared to Placebo delivered intrathecally three times, two months apart, to participants with early ALS.

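### The SAP's adverse event tables pool all three injection periods, so the planned AE output will not show whether AE incidence changes with the second and third injection.

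*SAP*

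**What the plan says.** SAP 2 gives the purpose of the trial as to "evaluate the efficacy and safety of three repeated administrations of NurOwn® (MSC-NTF cells) as compared to placebo", and SAP 3.1 states the goal in similar terms. Protocol 1.1 describes the first-in-man study and the US Phase 2 trial as single-dose studies.

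On adverse events, SAP 9.1.1 sets these rules:

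- **Window.** A TEAE is "an AE that occurs for the first time after initiation of treatment", or an earlier event that worsens afterwards. The clock starts at the first injection and does not restart.
- **Counts, by System Organ Class and Preferred Term.** "The above summaries will include the number of events as well as number and percentage of subjects experiencing at least one TEAE".
- **Repeats.** "A subject who experiences multiple TEAEs coded to the same Preferred Term within the same SOC will be counted only once for that Preferred Term".
- **Severity.** Summarised at the maximum.
- **Denominator.** The arm's safety population, which SAP 6.5.1 defines as those with at least one treatment.

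The tables are broken down by seriousness, severity, relatedness and procedure-relatedness. None is broken down by injection or interval. Protocol 1.9.3.5 has the same structure. SAP 9.2 tabulates the number of injections received but does not link it to AEs.

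Later injections are conditional. Protocol 1.3.3.2 says: "Participants will be eligible for their 2nd and 3rd treatments if, in the judgment of the study team, there are no medical contraindications to proceeding". Protocol 1.8.2 has the date and time of AE onset recorded.

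**The concern.** Repeat dosing is what is new here compared with the single-dose trials. A reader of the report will want to know whether reactions lessen, stay level or worsen as intrathecal exposure accumulates. A table that pools Week 0 to Week 28 reports one figure per term and arm for the whole regimen. It answers whether NurOwn participants had more events than placebo participants. It does not say after which injection those events came. If risk were concentrated after the third injection, it would appear as an ordinary overall rate.

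**Working it through.** **Inputs.** The documents state no AE rate and no rate of missed injections, so all risks and dosing numbers below are assumptions. The arm size of about 100 comes from the efficacy calculation in SAP 4.3 (35% vs 15%, two-sided 0.05, 90% power). That figure reproduces with the chi-square formula without continuity correction:

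n = [1.960·√(2·0.25·0.75) + 1.282·√(0.35·0.65 + 0.15·0.85)]² / 0.20² = 96.4, so 97 per arm.

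**Step 1: what the planned measures can see.** Let r1, r2, r3 be the risks of a given term after each injection. Assume independence, at most one event per interval, and all three injections given. Then:

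- ever-incidence = 1 − (1−r1)(1−r2)(1−r3)
- events per 100 = 100·(r1+r2+r3)

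| Assumed risks | Ever-incidence | Events per 100 |
|---|---|---|
| 10/25/49% | 1 − 0.90·0.75·0.51 = 65.6% | 84 |
| 49/25/10% | 1 − 0.51·0.75·0.90 = 65.6% | 84 |
| 30/30/30% | 1 − 0.70³ = 65.7% | 90 |
| 30/45/60% | 1 − 0.70·0.55·0.40 = 84.6% | 135 |

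Rows 1 and 2 are opposite patterns with identical output. The formulas do not depend on the order of the injections, so this is not peculiar to the chosen rates: 10/20/28.9% and its reverse both give 48.8% and 58.9 events per 100. Row 4 shows the limit of the argument. A rise from the same starting risk as row 3 does raise both totals, but the table does not show which injection produced the excess.

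**Step 2: incomplete dosing.** Suppose 100, 90 and 80 participants receive injections 1, 2 and 3. The event totals for rows 1 and 2 become:

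- rising: 10 + 90·0.25 + 80·0.49 = 71.7
- falling: 49 + 90·0.25 + 80·0.10 = 79.5

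The totals now differ, but the rising pattern has the smaller one, so the total still gives no clue to direction.

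**Step 3: denominator for an interval table.** With a constant 20% risk among those dosed and the same 100/90/80, dividing by the full safety population gives 20%, 18% and 16%. That is a false decline. Dividing by those given the injection gives 20% each time.

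**Step 4: what interval tables would deliver.** The 95% half-width is 1.96·√(p(1−p)/n). At p = 20% it is ±7.8 points for n = 100 and ±8.8 for n = 80. Treating injection 1 (n = 100) and injection 3 (n = 80) as unpaired, approximate power is 48% for a rise from 10% to 20%, 76% for 10% to 25%, and 92% for 10% to 30%. The tables would be descriptive, but informative for large changes.

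**The case against.** The strongest reply is that the safety objective in Protocol 1.2.1 is NurOwn versus placebo on AE incidence, and the overall table by arm addresses that for the regimen as a whole. An injection-order gradient is not a stated objective. This stands, and it is why the addition is descriptive and the overall tables stay.

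A reader might also infer three stronger things that the documents do not support.

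- **That the trial cannot show rising harm.** It can. Onset and injection dates allow the analysis. Listings carry days from first treatment where applicable (SAP 6.1). Laboratory results, vital signs, examinations and ECG are summarised by visit (SAP 9.4 to 9.7). These outputs do not give AE incidence by injection, but the omission is one of tabulation, not of design.
- **That ever-incidence is nearly the same whatever the trend.** This holds only for chosen patterns, as row 4 of the table shows. The event count is also planned, so recurrences are not lost; they are only undated in the summary.
- **That participants who react early and stop dilute the result.** They stay in the denominator, but they are in the ever-affected numerator too. The denominator becomes a fault only if it is carried into an interval table.

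Finally, the table shells mentioned in SAP 6.4 are not among the documents, and SAP 2 allows further analyses before lock. So the claim is limited to what the SAP text specifies.

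**Conclusion.** The point holds for the AE summaries. As written, SAP 9.1.1 gives one pooled period per arm, and neither of its two measures responds to the order of per-injection risks. The planned AE output therefore will not show whether incidence changes with the second and third injection. The size is illustrative: a nearly five-fold rise and a nearly five-fold fall (10/25/49% and its reverse) produce the same 65.6% and 84 events per 100, given independence and complete dosing. The efficacy results are unaffected, as is the overall safety comparison between arms. It is a cheap improvement to make before unblinding, because it bears directly on the repeat-dose question that the trial sets itself.

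**What to change.** Keep the overall tables. Before unblinding, add to SAP 9.1.1:

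1. **Interval tables by arm** for all TEAEs, serious, treatment-related and procedure-related TEAEs, and TEAEs by severity. The intervals are T1 to before T2, T2 to before T3, and T3 to end of study. The denominator is participants who received that injection. Count a participant once per term within each interval, so that a recurrence after a later injection is seen.
2. **Event rates per person-time**, because the intervals are about 8, 8 and 12 weeks and vary with manufacturing and COVID-19 delays.
3. **Onset within a short common window after each injection**, for example 7 days. A 4-week window would not be like-for-like: only the first injection is followed by a Week 2 visit with a lumbar puncture (Protocol 1.5.1 and 1.5.5.2). Seven days closes before that visit (14 − 3 = day 11 at the earliest).
4. **Reading rule.** Compare NurOwn with placebo within each interval, since disease progression also changes AEs over time.
5. **Partial dates.** State how they are assigned to intervals. SAP 6.8.3 sets a missing onset day to the 1st of the month (or to the first dose date in that month). For example, an event after a mid-month second injection could then fall into the first interval.

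The cost is SAP wording and a rerun of existing table programs with a period variable; no new data are needed. The downsides are more tables, and later intervals that are descriptive and include only participants who went on to further injections.

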### **9.1.2. Missing and Partial AE Onset Dates**

The missing and partial AE onset dates will be imputed as described in [Section 6.8.3](#).

## **9.2. Exposure and Compliance to Study Drug**

A summary of the number of intrathecal administrations received will be presented using counts and percentages for the Safety Population. The duration in months (exposure) between the first and third intrathecal administration will be presented using descriptive statistics for the Safety population.

Compliance rate (%) will be calculated for each subject as follows:

$(\text{Total number of intrathecal administrations}) / (\text{Expected number of administrations}) * 100.$

## **9.3. Concomitant Medications**

Concomitant medications are those given to the subject during or after the first transplantation. All concomitant medications will be recorded.

Participants who were on a stable dose of riluzole for at least 30 days prior to screening will continue taking riluzole prior to study enrolment, unless requiring discontinuation during the study for standard side-effects. In addition, the use of non-invasive procedures including continuous positive airway pressure and diaphragmatic pacing systems will be recorded. The analysis of Concomitant medication is provided in [Section 7.6](#).

## 9.4. Routine Laboratory Data

Clinical Laboratory Tests include:

Hematology: Complete blood count (CBC) (Red blood cells [RBC] with Indices, White blood cells [WBCs] with differential and platelet count, hemoglobin [Hb], hematocrit [Ht]).

Blood Biochemistry: Sodium (Na), Potassium (K), Calcium (Ca), Bicarbonate (HCO3), blood urea nitrogen (BUN), Creatinine (Cr), Glucose (Gluc), Chloride (Cl), Magnesium (Mg), Phosphorus (Phos), total protein, triglycerides (TG), Total cholesterol, high-density lipoprotein (HDL), low-density lipoprotein (LDL), urea, total bilirubin, aspartate aminotransferase (glutamic oxaloacetic transaminase) (AST[GOT]), alanine aminotransferase (glutamic pyruvic transaminase) (ALT[GPT]), alkaline phosphatase (ALP), uric acid.

Coagulation: Prothrombin time, Partial thromboplastin (PTT).

Urinalysis - Specific Gravity, pH, glucose, protein, ketones, blood.

Infectious Diseases/Virus: Hepatitis B and C (HBV, HCV), Human immune deficiency virus 1 and 2 (HIV 1 and 2).

All test results and associated normal ranges from central laboratories will be reported in the standard International System of Units (SI unit). Continuous values will be summarized using descriptive statistics and categorical values, including low, normal, and high results with respect to reference ranges will be tabulated at each visit and treatment group.

Change from Baseline for continuous values will be summarized using both continuous summary statistics as well as shift tables based on normal ranges at each post-Baseline visit.

Shift from Baseline tables will also include shift from Baseline to the worst-case post-Baseline.

## 9.5. Vital Signs

The following vital signs will be collected per the schedule of assessments using the given units:

- Heart rate (beats per minute)
- Systolic blood pressure (mmHg)
- Diastolic blood pressure (mmHg)
- Respiration rate (breaths per minute)
- Body temperature (Celsius)
- Body Weight (kg)

Vital signs will be summarized with continuous descriptive statistics at each visit by treatment group as described in Table 2. Change from Baseline will also be summarized to each post-Baseline Visit and at 2, 4, 8, 20, and 24 hours, post-transplant or 72 hours' post transplantation.

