
Safety
	
All safety analyses will be conducted on the Safety Population, which will be defined as all participants who were randomized and had at least one treatment performed.
 
When evaluating changes in safety parameters, Baseline will be defined as the last measurement prior to the first treatment.
 
For physical examination, concomitant medications, hematology and blood chemistry, ECG assessments, shifts from baseline in categorization of results (e.g. normal/abnormal or above/below normal range) will also be summarized.
 
All continuous data obtained in this study and documented in the electronic case report forms (eCRFs) will be listed and tabulated with descriptive group statistics (n, mean, standard

	deviation, median, minimum, maximum). For discrete data, counts and percentages will be summarized.
Biomarkers	CSF and/or serum or blood samples will be analyzed for the concentration of biomarkers and their relationship to efficacy outcomes. In addition, relationships between neurotropic factors, inflammatory markers and clinical outcomes will be evaluated to determine if any biomarkers can be predictive to treatment outcome or prognostic to disease progression.

TABLE OF CONTENTS

STUDY SYNOPSIS	6
TABLE OF CONTENTS	13
ABBREVIATIONS.....	15
1. CLINICAL STUDY PROTOCOL.....	17
1.1 INTRODUCTION	17
1.1.1. COVID-19 Pandemic.....	18
1.2 STUDY OBJECTIVES	19
1.2.1. Primary objectives	19
1.2.2. Secondary Objectives	19
1.3 INVESTIGATIONAL PLAN.....	20
1.3.1 Overall Study Design and Plan.....	20
1.3.2 Study Schematic	21
1.3.3 Treatment Plan.....	22
1.3.4 Blinding and Randomization	22
1.3.5 Duration of study	23
1.3.6 Discussion of Dose	23
1.3.7 Discussion of Study Design, Including Choice of Control Group	24
1.4 PATIENT POPULATION.....	24
1.4.1. Inclusion Criteria	24
1.4.2. Exclusion Criteria	25
1.5. STUDY ASSESSMENTS	26
1.5.1. Anticoagulation therapy.....	26
1.5.2. CSF and Blood collection for assessments of Biomarkers.....	27
1.5.3. Genetic Analyses	27
1.5.4. Clinical Laboratory Safety Tests	27
1.5.5. Physical Examinations, Vital Signs, and Electrocardiograms.....	27
1.5.6. Pre-transplantation Visits.....	28
1.5.5. Transplantation Visits.....	30
1.5.6. Post transplantations follow-up	35
1.5.7. Safety Follow-Up.....	36
1.5.8. Lost to Follow-Up	36
1.6. INVESTIGATIONAL PRODUCT INFORMATION	37
1.6.1. General Information.....	37
1.6.2. NurOwn® (MSC-NTF cells) Product Characteristics.....	37
1.6.3. Treatment Compliance.....	38

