1.5.5.4. Visit 9: 2nd Cell Transplantation (Week 8 \pm 5 days)

At the second transplantation visit, coordinated with patient-assigned manufacturing slots, participants will be admitted to an inpatient study unit for study procedures (See Tables 1 and 2).

Pre-transplant assessments (Up to 8 hours before transplant - Estimated Time 06:00-14:00) will include:

- Admit to Inpatient Ward
- Body weight measurement
- Directed physical examination
- Vital sign measurements (including blood pressure, body temperature; pulse and respiration rate after sitting for at least 3 minutes)
- ALSFRS-R questionnaire
- SVC pulmonary function test (if permitted)
- Neurological examination
- Review of concomitant medications
- Blood for hematology, coagulation, biochemistry, and biomarker evaluations; as well as urinalysis will be collected
- Review of adverse events
- Standard 12-Lead ECG

Following pre-transplant procedures, participants will undergo (Hr. 0 - Estimated Time 12:00):

- Immediately prior to the IT administration of cells or placebo, CSF will be removed and retained for analysis.
- IT injection of cells or placebo.

Concomitant medications and AEs will be monitored throughout the study visit, as necessary.

Post-transplant, participants will undergo the following:

- Vital signs will be monitored at 2, 4 (\pm 15 mins.), 7, 20, and 24 hours (\pm 30 mins.), post-transplant and/or upon discharge at 24 hours or up to 72 hours post transplantation. Inpatient observation is up to 72 hours, with earlier discharge at investigator discretion.
- Visual inspection of the injection site will be performed at 2 (\pm 15 mins.), and 20 (\pm 30 mins.) hours post-transplant.
- Blood for hematology, coagulation, biochemistry, and biomarker evaluations; as well as urinalysis) will be collected 20 hours (\pm 30 mins.), post-transplant.

Prior to discharge, assessments will include:

- Vital sign measurements (including blood pressure, body temperature; pulse and respiration rate after sitting for at least 3 minutes)
- Directed physical examinations will be performed at 24 hours or up to 72 hours post transplantation).
- Review of concomitant medications
- Review of adverse events
- Discharge from Inpatient Setting

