- 12 An ET visit will be conducted only for participants who discontinue the study after treatment, post Visit 6. The ET visit will include all the procedures required at study Visit 14. For participants who refuse further clinic study visits, telephone contact by study staff shall be attempted and documented to review for adverse events at each scheduled visit through the remainder of study.

Table 2 Detailed Schedule of Assessments for Cell Transplantation Visits (V6, V9 and V11)

Estimated Time	06:00-14:00	12:00-14:00	14:00-16:00	16:00-18:00	19:00-21:00	08:00-10:00	12:00-14:00	
Time\ Procedure	Up to 6 hours before transplant	Hr. 0	Hr. 2 (±15 min)	Hr. 4 (±15 min)	Hr. 7 (±30 min)	Hr. 20 (±30 min)	Approximately Hr. 24 (±30 min)	Hr. ≥ 24-72 (before discharge ±30 min)
Admit to Inpatient Ward	√							
Body weight	√							
Physical Examination	√						√	
Vital signs ¹	√		√	√	√	√	√	√
12 lead ECG ²	√ ²						√ ²	
ALSFRS-R	√							
Slow Vital Capacity (SVC)*	√							
Neurological Examination	√							
Concomitant medication review ³	√		√	√	√	√	√	√
Hematology ⁴	√					√		
Blood biochemistry ⁵	√					√		
Urinalysis ⁶	√					√		
Coagulation ⁷	√					√		
Blood collection for biomarkers ⁸	√					√		
Cell Transplant IT ⁹		√						
Retention of CSF sample		√						
Visual inspection of injection site			√			√ ⁹		
Adverse events review ³	√		√	√	√	√	√	√
C-SSRS ¹⁰	√							
Assessment of blinding (Participant and Investigator) ¹¹								√
Discharge from Inpatient Setting								√

Brainstorm Cell Therapeutics		
Phase 3 Clinical Protocol BCT-002 US Amendment 2.1: March 2020	NurOwn® (MSC-NTF cells)	Page 62 of 66

Abbreviations: ALS=Amyotrophic Lateral Sclerosis; ALFRS-R=ALS Functional Rating Scale–Revised; CSF=cerebral spinal fluid; C-SSRS=Columbia-Suicide Severity Rating Scale ECG=electrocardiogram; IT=intrathecal

* SVC will be performed when permitted, following resolution of COVID-19 per institutional guidance

- 1 Pulse rate, Blood pressure, Respiratory rate, Body temperature at the designated time-points. At 2, and 4 hours \pm 15 minutes. At 8, 20 and 24 hours \pm 30 minutes
- 2 ECG will be performed at Visits 6, 9 and 11 – Time Window: +/- 30 min.
- 3 Concomitant medications and AEs will be monitored and ongoing data will be collected throughout the study visit, as necessary
- 4 Hematology: Complete blood count (Red blood cells with Indices, white blood cells with differential and platelet count, hemoglobin, hematocrit) - Time Window: +/- 30 min.

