## **6.6. Baseline Definition**

The baseline visit will be defined as the last non-missing measure prior to initiation of investigational treatment (first treatment at Visit 6, Week 0).

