### 6.7.3. Change and % Change from Baseline

Baseline is defined as the last non-missing observation prior to first study drug administration.

Change from baseline is calculated as (post-baseline result – baseline result).

If either the baseline or the post-baseline result is missing, the change from baseline is set to missing as well.

If the baseline result is missing or 0, or if the post-baseline result is missing, then % Change from Baseline will be set to missing at that visit.

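### SAP 9.5 takes the hourly vital-sign changes after the second and third injections only against the pre-Visit 6 baseline; a change from the same-visit pre-transplant value should be added

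*SAP*

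**What the plan says.** The SAP uses a single baseline. Section 6.6 states: "The baseline visit will be defined as the last non-missing measure prior to initiation of investigational treatment (first treatment at Visit 6, Week 0". Section 6.7.3 repeats it for change scores, "Baseline is defined as the last non-missing observation prior to first study drug administration", and gives the formula: "Change from baseline is calculated as (post-baseline result – baseline result".

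Section 9.5 applies this to vital signs: "Change from Baseline will also be summarized to each post-Baseline Visit and at 2, 4, 8, 20, and 24 hours". The sentence goes on to a time point of up to 72 hours and names no other reference value. The same section also plans the values themselves: "Vital signs will be summarized with continuous descriptive statistics at each visit by treatment group as described in Table 2".

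The Protocol synopsis agrees with the SAP: "When evaluating changes in safety parameters, Baseline will be defined as the last measurement prior to the first treatment". Protocol 1.9.3.5 is looser. It places the safety baseline before transplantation without saying which of the three transplantations is meant.

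Vital signs are taken both before and at intervals after the injection at Visits 6, 9 and 11 (Protocol Table 2 in Appendix 1; SAP Table 3). The Visit 9 text schedules "Pre-transplant assessments (Up to 8 hours before transplant" and lists vital signs among these assessments. Visit 11 does the same, while the table column reads "Up to 6 hours before transplant".

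**The concern.** Vital signs at 2 to 24 hours after an intrathecal injection are there to show the acute response to that injection. At Visit 6 the planned change does this, because the baseline is normally the pre-dose value of the same visit. At Visits 9 and 11 the same label covers a different quantity: the acute response plus whatever has changed since Visit 6, such as progression, weight, medication or a lasting effect of the preceding injection.

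Repeat dosing is what this trial adds to the randomised US Phase 2 study, which gave a single dose (Protocol 1.1). Acute tolerability of the second and third injections is therefore where new safety information arises, and the planned change summaries do not show it directly.

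**Working it through.** The plan has no figure to reproduce here, and the documents give no SD, correlation or drift for any vital sign. The check traces the reference value and then works through what follows from it.

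**1. Age of the reference.** Injections are at Weeks 0, 8 and 16 (Protocol 1.3.5). With the baseline fixed before the Week 0 injection:

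- Visit 6: same visit.
- Visit 9: 8 − 0 = 8 weeks.
- Visit 11: 16 − 0 = 16 weeks.

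These are nominal. SAP 6.5 reports longer intervals between visits because of COVID-19 and manufacturing constraints, and the schedule footnotes allow flexible windows for the transplantation visits. A same-visit pre-transplant value would be at most 6 or 8 hours old. The Protocol gives both limits and they should be reconciled, but the argument is the same under either.

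**2. What the planned change contains.** For visit v and post-dose hour h:

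Y(v,h) − Y(V6,pre) = [Y(v,h) − Y(v,pre)] + [Y(v,pre) − Y(V6,pre)] = acute change + drift.

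At Visit 6 the second term is zero. Illustration for Visit 9, with assumed values in arbitrary units:

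| Acute | Drift | Planned mean change | Same-visit mean change |
|---|---|---|---|
| 0 | 0 | 0 | 0 |
| 0 | 3 | 3 | 0 |
| 0 | 6 | 6 | 0 |
| 5 | 0 | 5 | 5 |
| 5 | 3 | 8 | 5 |
| 5 | 6 | 11 | 5 |

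Within one arm, drift enters the planned figure in full.

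**3. What other planned outputs recover.** SAP 9.5 also plans change from baseline to each visit. If the visit value is the pre-dose one and the same subjects contribute, its mean equals the drift. Hourly mean change minus visit mean change then returns the acute mean, for example 11 − 6 = 5. If mean drift is the same in both arms, it also cancels in the NurOwn minus placebo difference.

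**4. Precision.** With a common SD σ and correlation ρ between the two measurements, the SD of a change is σ√(2(1 − ρ)). Assume σ = 10, ρ of 0.7 to 0.9 within a visit and 0.3 to 0.6 across 8 to 16 weeks.

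- Same-visit change: 10√(2 × 0.3) = 7.7 down to 10√(2 × 0.1) = 4.5.
- Change from Visit 6: 10√(2 × 0.4) = 8.9 up to 10√(2 × 0.7) = 11.8.
- Ratio: √(0.4/0.3) = 1.15 to √(0.7/0.1) = 2.65.
- Standard error of an arm difference with 100 per arm, SD × √(2/100): 0.63 to 1.10 same-visit, against 1.26 to 1.67 from Visit 6.

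The top ratio pairs the highest within-visit with the lowest long-term correlation. The direction rests only on the within-visit correlation being the higher of the two.

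**5. How many summaries.** If the five time points from 2 to 24 hours are shown separately for three injections, there are 5 × 3 = 15 change summaries, of which 5 × 2 = 10 use the older reference. SAP 9.5 does not say that they are shown by injection. If they are pooled, a single row would mix references of different ages.

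**The case against.** A reader might infer that the acute effect of the second and third injections cannot be separated from drift. The documents do not support that. Pre-dose vital signs are collected at Visits 9 and 11, values and changes per visit are summarised by arm, and subject listings are planned (SAP 6.1). Both arms also have the same procedure at the same visits. The mean acute change can be approximated as in step 3 of the working.

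The approximation has limits. SAP 9.5 does not say which of the several measurements at a transplantation visit is the visit value. Subtracting means gives no SD, quartiles or extremes of individual acute change. The placebo contrast removes drift only if it is equal in both arms, and it also removes any procedure effect common to both arms. SAP 9.1.1 treats that effect as of interest, since it tabulates procedure-related events separately.

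A reader might also infer that the Visit 6 reference is wrong and should be replaced. That does not follow either. A lasting shift after the first or second injection would sit inside the pre-dose value at Visit 9 or 11. With a same-visit reference alone, the hourly tables would no longer show total departure from the untreated state, which is a fair safety question under repeat dosing. This part of the objection stands, and it is why the remedy adds a reference and keeps the existing one.

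Finally, detection of acute reactions does not rest on this table alone. Adverse events are reviewed at each post-dose time point, and the Protocol's vital-signs section sets absolute categories of clinical concern. This also stands and limits the importance of the point.

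**Conclusion.** The point holds as a minor one. On a plain reading of SAP 6.6, 6.7.3 and 9.5, the hourly vital-sign changes at Visits 9 and 11 use a reference nominally 8 or 16 weeks old, and no change from the same-visit pre-transplant value is planned. The change summaries for two of the three injections therefore combine acute response and drift, and they are likely noisier than they need be. The ratio of 1.15 to 2.65 rests wholly on assumed correlations, and the drift values are illustrations. This is a descriptive safety display: no endpoint, test, error rate or data collection is affected.

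**What to change.** In SAP 9.5, for all post-transplant time points at Visits 6, 9 and 11, add change from the last non-missing pre-transplant value of the same visit, summarised by arm and by injection. Keep the change from the Visit 6 baseline alongside it. State that the hourly results are shown separately for each injection, and which measurement at a transplantation visit counts as the visit value. Align the safety-baseline wording in the Protocol synopsis and Protocol 1.9.3.5, so that both say which transplantation is meant.

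The cost is one derived reference variable and one further table from data already collected. The change should be made before database lock and unblinding, the point by which the SAP (section 2) says any further changes will be made.
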